The following outcomes will be assessed:

PRIMARY

1. 30 ± 6 days *first occurrence* of post-discharge **HF-related** HCRU; defined as hospitalization, emergency department [ED] visits, death or cardiac transplantation/ ventricular assist device [VAD] implant-- individual components and combined),

SECONDARY:

2. 90- and 180-day ± 6 days *first occurrence* of post-discharge **HF-related** HCRU; defined as hospitalization, emergency department [ED] visits, death or cardiac transplantation/ ventricular assist device [VAD] implant-- individual components and combined),
3. 30-, 90- and 180-day ± 6 days *first occurrence* of post-discharge **all-cause** HCRU; defined as hospitalization, emergency department [ED] visits, death or cardiac transplantation/ ventricular assist device [VAD] implant-- individual components and combined),
4. 30-, 90- and 180-day ± 6 days *time to* first occurrence of **all-cause** and **HF-related** post-discharge HCRU (individual components and combined),
5. 30-, 90- and 180-day ± 6 days *total all-cause* post-discharge HCRU (individual components and combined);
6. 30-, 90- and 180-day ± 6 days *total HF-related* post-discharge HCRU (individual components and combined);

NCT-03657459

7. Change in *functional status* from baseline to 30-, 90- and 180-days \pm 6 days after hospital discharge,
8. Change in *dyspnea scores* from baseline to 30-, 90- and 180-days \pm 6 days after hospital discharge,
9. Change in *fatigue scores* from baseline to 30-, 90- and 180-days \pm 6 days after hospital discharge, and
10. Change in *self-efficacy for managing symptoms* from baseline to 30-, 90- and 180-days \pm 6 days after hospital discharge
11. Differences in primary and secondary outcomes (1-10) among *intervention-group participants*, after creating 3 sub-groups based on post-discharge video viewing ([a] total number of times videos were watched, [b] viewed by caregivers/family in the hospital, and [c] viewed by caregivers/family post hospital discharge.

Specific aims and hypotheses:

1. Determine the effects (and time to effects) of HF danger signs education on *first occurrence*, *time to first occurrence* and *total* all-cause and HF-related HCRU after hospital discharge: hospitalization, ED visit, death, cardiac transplantation or VAD.
2. Examine if functional status, dyspnea, fatigue and self-efficacy for managing symptoms scores change over time and the direction of change.

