Hypothesis 3c: Repeat viewing of videos by patients, compared to 1-time viewing in-hospital and/or viewing of videos by family supporters/caregivers in hospital and/or post discharge, compared to viewing only by patients, will be associated with *higher self-efficacy for HF self-care actions* (due to symbolic modeling of self-care actions)

METHODS

Design: The study will use a 2-group, randomized, placebo-controlled, single blinded, design. Healthcare providers and unit nurses will be blinded to group assignment, but may learn about HF danger signs education if they enter the patients' room during intervention delivery or discuss the intervention prior to hospital discharge.

In brief, the research intervention involves 3 novel short videos (fatigue, dyspnea and edema) that will be viewed back-to-back by intervention group patients using a DVD player. Wellflix, Inc. videos are research-informed, use behavioral-modeling, are personally-tailored and are available 24/7 online. Patients will receive a handout sheet with the web address to view the videos after discharge and will be encouraged to view them with family members.

Sample (including sample size calculation) and Setting

A total of 732 patients will be enrolled (366 per group) and consist of adults with chronic HF (diagnosis \geq 2 months) who are hospitalized for acute decompensated HF within Cleveland Clinic Hospitals. This sample size includes a 10% attrition rate. Sample size was based on power calculations using 30-day first occurrence of HF-related HCRU (hospitalization, emergency department visit, mortality, cardiac transplantation or VAD). The current expected 30-day HF-related readmission rate is 20% among the control group. Allowing for other HCRU components, a control group HCRU rate of 28% is expected at 30 days. At 90 days, HCRU rate of 46% is expected in the control group. Sample size calculations were performed using SAS software (version 9.4; Cary, NC) and assume use of two-sided Pearson -chi square tests. With 329 patients in each group there will be 80% power to detect a 33% relative decrease (9.2% absolute decrease) in first occurrence of HF-related HCRU from a HCRU rate of 28% in the control group. With this sample size there would also be 85% power to detect a relative decrease of 25% (absolute decrease of 11.5%) from a control group event rate of 46% at 90-days. Allowing for 10% loss to follow-up, we will enroll 366 patients per group (732 total).

NCT-03657459

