The fatigue and dyspnea video's will be viewed back-to-back and the edema video will be added for patients with a history of edema. There are 4 versions of each video: (1) based on race (Caucasian and African-American) and sex (male and female)—to promote symbolic modeling— by patients who look like video models (as stated in the introduction). Scripts for each video were developed jointly by [name], Director of Media and Education for Wellflix, Inc. and [name] PhD, principal investigator and clinical nurse specialist in HF. Content includes recognition and assessment of fatigue, dyspnea and edema and specific actions to take to reduce the danger signs or prevent worsening (dietary sodium and/or fluid restriction, physical activity/exercise and contacting the doctor).

Overall video viewing time for all 3 videos is 9:50 minutes; the fatigue and dyspnea videos that all intervention patients will view are 6:50 minutes:

- *Fatigue* is 2:20 minutes + end text list= 3:00 minutes;

NCT-03657459

- *Dyspnea* is 1:40 minutes + dyspnea “yes” or “no” management (2 options; patient selects the option that matches current status) = 3.50 minutes
- *Edema* is 2:40 minutes + end text list= 3:00 minutes;

During hospitalization, videos will be loaded into an iPAD and will be viewed through the iPAD.

Patients have an opportunity to view videos post-discharge as desired and able. *Post discharge*, videos can be in 2 ways: (1) via the Wellflix, Inc. site at www.wellflix.net/DangerSignsCC or (2) by DVD player (DVD created by Wellflix, Inc for this research), for patients who have DVD player capability and prefer this method.

NOTE, at/after 180-day follow up data are collected, *usual care group* patients will be offered access to Wellflix, Inc. videos used in this research study via mailing of a handout sheet developed specifically for them (that contains the web address and a note of encouragement to view the videos.

Outcomes and Measurement

HCRU. Includes all-cause and HF-related hospitalization, ED visit, death, cardiac transplantation, or VAD placement at 30-, 90-, and 180-days \pm 6 days in both groups. Data will be retrieved from medical records when available or via telephone call to patients.

- Patients will receive a calendar to keep track of HCRU events in-between phone calls.
- Research nurses will use a case report form to record HCRU events

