Patient characteristics will be summarized overall and by randomized group using frequencies and percentages for categorical factors and means and standard deviations for continuous measures. First occurrence HCRU use (**all-cause and HF-related**) will be compared using Pearson chi-square tests. Time to first HFCU use will be summarized using Kaplan-Meier estimates, and compared using log-rank tests and Cox proportional hazards models. Total HCRU use will be compared using Poisson regression models. Linear mixed effect models will be used to evaluate trends in functional, dyspnea, fatigue, and self-efficacy measures over time and, if trends significantly differ, comparisons within time point will be performed. Secondary analyses will use similar methods to compare patients in the video group, stratified by video viewership, on the same outcomes. If appropriate, exploratory analyses will also be performed, comparing the above outcomes between treatment groups, adjusting for any patient characteristics that differ between randomized groups. Analyses will be performed using SAS software (version 9.4; Cary, NC), and an overall significance level of 0.05 will be assumed for all endpoints. Comparisons between the 3 subgroups of patients in the video group will use Bonferroni corrected significance criteria to preserve the overall error rate when making multiple comparisons.

Feasibility

The main campus of Cleveland Clinic has a high volume of HF discharges each year. Other hospitals in the system have moderate volumes of HF discharges, and are less likely to have patients who meet exclusion criteria due to enrollment in another research study or non-ambulatory NYHA FC IV (advanced) HF. Electronic medical records allow for review of data on events that occur in *all* system hospitals and regional medical practice ambulatory care sites; decreasing the need to rely on patient recall of HCRU.

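### Kaplan-Meier summaries of time to first event overstate cumulative incidence for endpoints that leave out some deaths; cumulative incidence curves should replace them

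*Combined protocol and SAP*

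**What the plan says.** Secondary outcome 4 (Study Purposes) is "30-, 90- and 180-day ± 6 days *time to* first occurrence of all-cause and HF-related post-discharge HCRU (individual components and combined"). For all of these, the Analyses section says: "Time to first HFCU use will be summarized using Kaplan-Meier estimates, and compared using log-rank tests and Cox proportional hazards models". HFCU appears to be a slip for HCRU.

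The same events are also analysed as proportions: "First occurrence HCRU use (all-cause and HF-related) will be compared using Pearson chi-square tests".

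Death is one of the listed components. The outcome list reads "defined as hospitalization, emergency department [ED] visits, death or cardiac transplantation/ ventricular assist device [VAD] implant-- individual components and combined", and the same list serves the HF-related and the all-cause versions. Under Outcomes and Measurement, HCRU "Includes all-cause and HF-related hospitalization, ED visit, death, cardiac transplantation, or VAD placement". That wording suggests that the HF-related qualifier reaches death too, but neither place says so outright.

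The plan does not say how a death outside the endpoint is handled in the time-to-event analysis. It gives no censoring rule and names no competing-risk method.

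**The concern.** A patient who dies before a first hospitalization, ED visit or transplant/VAD can no longer have that event. Kaplan-Meier, as normally run, censors the patient at death and so treats the patient as someone who could still have the event later. One minus the Kaplan-Meier estimate is then the event probability in a hypothetical population without death, and it lies above the probability that patients actually face.

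The endpoints divide as follows:

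- **Affected under any reading:** hospitalization, ED visit and transplant/VAD as single components, both all-cause and HF-related.
- **Affected only if HF-related HCRU counts HF-related deaths alone:** the HF-related composite and HF-related death.
- **Not affected:** the all-cause composite and all-cause death.

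At stake are the curves and the 90- and 180-day rates read from them. A reader will take these as the share of patients who had the event. They will also sit beside first-occurrence percentages for the same endpoint, in which a patient who died first would ordinarily stay in the denominator as a non-event.

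**Working it through.** **1. The plan's own figures.** Inputs from the sample size section: control rate 28% at 30 days, 33% relative reduction (so 0.28 × 0.67 = 18.76%), 80% power, two-sided Pearson chi-square; significance level 0.05 from the Analyses section.

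n = [1.960 × √(2 × 0.2338 × 0.7662) + 0.8416 × √(0.28 × 0.72 + 0.1876 × 0.8124)]² / 0.0924² = (1.1732 + 0.5008)² / 0.008538 ≈ 328.2, so 329 per group, as stated.

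Allowing for attrition, 329/0.9 gives 366 per group and 732 in total, as stated. Power at 90 days for 46% versus 34.5% is 85.4%, against 85% stated. These calculations treat 28% and 46% as simple proportions, so I take them as true proportions and not as Kaplan-Meier values.

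**2. Excess of one minus Kaplan-Meier.** Let F1 be the true event proportion and F2 the proportion who die first of a death outside the endpoint. With proportional cause-specific hazards and no other censoring,

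1 − KM = 1 − (1 − F1 − F2)^(F1/(F1 + F2)).

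Worked case at 90 days with F1 = 0.46 and F2 = 0.10: 1 − 0.44^(0.46/0.56) = 1 − 0.44^0.8214 = 0.4905, an excess of 3.05 points (3.1 before rounding the estimate).

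F2 is assumed throughout, because the documents give no mortality figure. The 180-day F1 is assumed as well.

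| Endpoint | F1 | Assumed F2 | Excess of 1 − KM (points) |
|---|---|---|---|
| 30-day HF-related composite | 28% | 0.5-5% | 0.1 to 0.8 |
| 30-day HF-related readmission alone | 20% | 0.5-5% | 0.05 to 0.6 |
| 90-day composite | 46% | 1-10% | 0.3 to 3.1 |
| 180 days | 55-60% (assumed) | 3-15% | 1.1 to 7.0 |

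The composite rows apply only if non-HF deaths fall outside the HF-related composite.

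**3. Sensitivity to timing.** If every competing death came before any event, 1 − KM would be F1/(1 − F2). For 28% with 5% deaths, 0.28/0.95 gives an excess of 1.5 points. For 46% with 10% deaths, 0.46/0.90 gives 5.1 points. These are extremes.

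**4. Difference between arms.** With 2-5% competing deaths in both arms, the planned 9.2-point difference at 30 days becomes 9.3-9.5 points, and the 11.5-point difference at 90 days becomes 11.7-11.9.

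**5. Loss to follow-up.** This also separates the two summaries. Suppose 10% are lost evenly over the interval and counted as non-events. With a = −ln(1 − F1) and c = −ln(0.9), the crude proportion is a/(a + c) × (1 − e^−(a+c)). That is 26.7% against a Kaplan-Meier value of 28% at 30 days, and 43.9% against 46% at 90 days, with no competing deaths at all.

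**The case against.** The strongest reply is that the plan already supplies the right rates. First occurrence, by component and combined, is compared by chi-square at each time point, and with complete follow-up the crude proportion equals the Aalen-Johansen estimate. Hypothesis 1b asks whether time to first event is longer, which log-rank and Cox address validly as comparisons of cause-specific hazards. What is left is a descriptive curve for one secondary outcome. Patients in hospice or palliative care, or with a condition implying survival under a year, are excluded, so competing mortality may be at the low end of the assumed ranges.

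Most of this stands and limits the point. It does not rescue the curve, which would still be read as the share of patients with an event and would still be too high.

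A reader might infer more than the documents support:

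- **That the plan states deaths will be censored.** It does not; this follows from the usual practice of the method named.
- **That the HF-related composite is certainly biased.** If any death counts in it, it has no competing death.
- **That competing deaths explain the whole gap between the curves and the chi-square percentages.** The 2.1 points from loss to follow-up at 90 days is as large as much of the competing-death range.
- **That the primary result or the arm comparison is compromised.** The primary endpoint is a 30-day proportion tested by chi-square, and the differences in step 4 barely move when mortality is equal in the two arms.
- **That log-rank should give way to Gray's test.** Gray's test answers a different question and can itself be moved by a mortality difference.

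**Conclusion.** The point holds for the Kaplan-Meier summaries of endpoints that omit some deaths. This is certain for the non-death components if deaths are censored in the usual way. For HF-related endpoints that include death, it depends on the likelier but unstated reading that only HF-related deaths count.

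Under proportional hazards and assumed mortality, the overstatement is negligible at 30 days, modest at 90 days and potentially several points at 180 days. The true size depends on mortality figures that the plan does not give. The chi-square primary analysis, the sample size, and log-rank and Cox as cause-specific comparisons are unaffected. This is a correction to secondary reporting, worth making because it is cheap and the planned summary is biased in a known direction.

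**What to change.** In the Analyses section:

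1. State whether HF-related HCRU counts any death or only HF-related death.
2. For every time-to-first endpoint that does not include all deaths, replace the Kaplan-Meier summary with Aalen-Johansen cumulative incidence curves, with the excluded deaths as the competing event.
3. Keep log-rank and Cox for these endpoints, labelled as cause-specific, and state the censoring rule.
4. Keep Kaplan-Meier for the all-cause composite and all-cause death.
5. Gray's test may be added as supportive, not as a replacement.

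The cost is a few lines of plan text and a change in the survival program. No new data are needed, since deaths are already collected and events already have to be classed as HF-related or not. The downside is one more type of curve to explain. Some difference from the crude percentages will also remain because of loss to follow-up, and the report should say so.

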3. Among intervention group participants, determine if post-discharge re-viewing of danger signs education by patients and/or viewing content by family supporters is associated with differences in HCRU, functional status, dyspnea, fatigue and self-efficacy for managing symptoms, including time to effects.

Hypothesis 1a: 30-day post-discharge HCRU will be lower or trend toward lower, and 90-, and 180-day *first occurrence*, and *total* HCRU will be lower in the HF video danger education group compared to the usual care group.

Hypothesis 1b: *Time to first* HCRU occurrence will be longer at 30-, 90- and 180-days in the HF video danger education group compared to the usual care group.

Hypothesis 1c: *Total* HCRU will be lower at 30-, 90- and 180-days in the HF video danger education group compared to the usual care group.

Hypothesis 2a: *Functional status* scores improve at 30-days and remain lower over time in the HF video danger education group compared to the usual care group.

Hypothesis 2b: *Dyspnea* scores improve at 30-days and remain lower over time in the HF video danger education group compared to the usual care group.

Hypothesis 2c: *Fatigue* scores improve at 30-days and remain lower over time in the HF video danger education group compared to the usual care group.

Hypothesis 2d: *Self-efficacy for managing symptoms* scores are higher at 30-days and remain higher over time in the HF video danger education group compared to the usual care group.

NCT-03657459

Hypothesis 3a: Repeat viewing of videos by patients, compared to 1-time viewing in-hospital and/or viewing of videos by family supporters/caregivers in hospital and/or post discharge, compared to viewing only by patients will be associated with *longer time to first HCRU and lower total HCRU*.

Hypothesis 3b: Repeat viewing of videos by patients, compared to 1-time viewing in-hospital and/or viewing of videos by family supporters/caregivers in hospital and/or post discharge, compared to viewing only by patients will be associated with *improved functional status* and *dyspnea and fatigue scores* (due to heightened awareness of danger signs, heightened recognition of worsening of danger signs)

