Patients will have decompensated HF with preserved or reduced ejection fraction when hospitalized and New York Heart Association FC III or ambulatory IV symptoms. Diagnosis and etiology of HF will be confirmed in the electronic medical record prior to enrollment.

Inclusion Criteria:

1. Not referred for cardiac transplantation or ventricular assist device placement during the index hospitalization (OK to be assessed for future placement),
2. Minimum age 18 years (no upper age limit),
3. Cognitively intact and able to view videos (adequate eyesight and hearing) with correction, if needed,
4. Discharge to home, assisted living facility or to a family member's home and can control dietary sodium and fluids as needed,
5. Willing to participate; which may require up to three (3) follow-up telephone calls post-discharge.

Exclusions:

1. Chart documented psychiatric or cognitive conditions that limit ability to understand video content or adhere to self-care recommendations (Alzheimer's condition, dementia, schizophrenia, other neurological history that impairs memory or concentration),
2. Plans to discharge to skilled nursing facility or hospice care,
3. Receiving home hospice or palliative care; or has a medical condition reflecting less than 1 year of survival (cachexia, end stage liver disease or cancer or non-ambulatory New York Heart Association functional class IV HF),
4. Hospitalized but at admission, in New York Heart Association functional class I or II HF
5. Post-cardiac transplantation or ventricular assist device placement,
6. Currently enrolled in another experimental HF research study,
7. Chronic renal failure and receiving chronic hemodialysis therapy for an estimated glomerular filtration rate $< 15 \text{ mL/minute/1.73 m}^2$,
8. A non-traditional form of HF (hypertrophic or restrictive forms of cardiomyopathy, congenital heart disease or Takotsubo cardiomyopathy).

Intervention

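### Total HCRU is tested by Poisson regression with no allowance for dispersion, so at 90 days the nominal 5% test can exceed 5% if patients' event rates differ at least moderately

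*Combined protocol and SAP*

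**What the plan says.** Secondary outcomes 5 and 6 are the total all-cause and total HF-related counts at 30, 90 and 180 days, each described as "post-discharge HCRU (individual components and combined" (outcome list, Study Purposes). Under Outcomes and Measurement, HCRU "Includes all-cause and HF-related hospitalization, ED visit, death, cardiac transplantation, or VAD placement". The first two of these can recur. The other three happen at most about once per patient.

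Hypothesis 1c predicts that total "HCRU will be lower at 30-, 90- and 180-days in the HF video danger education group", and Hypothesis 1a also refers to totals. The Analyses section gives the method in one sentence, "Total HCRU use will be compared using Poisson regression models", and then says "Secondary analyses will use similar methods to compare patients in the video group" by viewership. Nothing in the document names a scale parameter, a robust variance, a negative binomial model, or a dispersion check with a fallback. The chi-square, log-rank and Cox analyses concern first events, so the Poisson model is the only planned test of totals.

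**The concern.** A Poisson model takes the variance of each patient's count to equal its mean. If some patients have persistently higher event rates than others, the counts vary more than that. Different rates are plausible here: the Sample and Setting section enrols "decompensated HF with preserved or reduced ejection fraction", in both NYHA class III and ambulatory class IV. The model-based standard errors would then be too small, the p-values too small and the confidence intervals too narrow.

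Two features push the other way. A patient cannot be readmitted while in hospital, and death ends the count. The net direction therefore has to be worked out, not assumed.

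At stake are the conclusions on total hospitalizations, ED visits and combined HCRU, both all-cause and HF-related, and the viewership comparisons that reuse the method. Death, transplantation and VAD taken singly are not part of the concern, because for an event that occurs at most once plain Poisson is conservative.

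**Working it through.** **Inputs from the plan.** The sample size section expects a 28% control rate of first HF-related HCRU at 30 days. For the later horizon it says "At 90 days, HCRU rate of 46% is expected in the control group". It gives no all-cause rate and no 180-day rate. Allocation is 366 per group and alpha is 0.05.

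**The plan's own figures reproduce.** 28% against 28% × 0.67 = 18.76% gives 329 per group (power 80.1%). 46% against 34.5% gives 85.4% power at 329. 329/0.90 = 365.6, so 366. The plan states no mean, variance or power for total counts.

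**Assumptions.** Patients' event rates follow a gamma distribution with mean 1 and variance k. Each horizon is calibrated separately so that the probability of at least one event equals the plan's rate p0.

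**Formulas, ignoring stays and deaths.**
- Mean count: μ = ((1 − p0)^(−k) − 1)/k, or −ln(1 − p0) at k = 0.
- Variance/mean: φ = 1 + kμ.
- True two-sided type I error: 2(1 − Φ(1.96/√φ)).

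Example, p0 = 0.46 and k = 1: μ = 1/0.54 − 1 = 0.852, φ = 1.852, 1.96/1.361 = 1.440, type I error 15.0%.

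**Adding stays and deaths.** I simulated 1,000,000 patients per cell with the same starting rates. No new event can occur for 7 days after each event, and a stated share of events ends the count. The resulting φ goes into the same formula. The 7 days and the 5% and 10% shares are assumptions.

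90 days, p0 = 46%, true type I error:

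| k | μ | φ | No stays or deaths | 7-day stays | Stays, 5% end count | Stays, 10% end count |
|---|---|---|---|---|---|---|
| 0 | 0.616 | 1.000 | 5.0% | 4.0% | 3.8% | 3.6% |
| 0.1 | 0.636 | 1.064 | 5.7% | 4.5% | 4.3% | 4.1% |
| 0.25 | 0.666 | 1.167 | 7.0% | 5.3% | 5.0% | 4.8% |
| 0.5 | 0.722 | 1.361 | 9.3% | 6.8% | 6.4% | 6.0% |
| 1 | 0.852 | 1.852 | 15.0% | 10.1% | 9.4% | 8.7% |

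(μ and φ are for the column without stays or deaths.)

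**30 days, p0 = 28%.** Ignoring stays and deaths, k = 0.25/0.5/1 gives 6.0/7.1/9.6%. With 7-day stays and 5-10% of events ending the count, it gives about 3.9%, 4.3-4.4% and 5.1-5.2%. The answer falls on either side of 5% depending on the assumption. The same is true of HF readmission alone ("The current expected 30-day HF-related readmission rate is 20% among the control group"): 5.7-8.0% without stays and 4.4-5.4% with 7-day stays, for k = 0.25-1.

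**Components that occur at most once.** Here φ = 1 − p. The type I error is 4.4% at p = 5% and 2.8% at p = 20%.

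**Robust variance.** I simulated 20,000 null trials per setting with 366 per arm, for k = 0, 0.25, 0.5 and 1, at 30 and 90 days, with and without 7-day stays and 5-10% of events ending the count (24 settings). Model-based Poisson rejected in 3.3-14.6% of trials; robust variance rejected in 4.8-5.4%.

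**The case against.** The strongest case against runs as follows. The size rests wholly on k, which the documents do not supply. The eligibility criteria also narrow the population: NYHA I-II, non-ambulatory class IV, hospice or palliative care, expected survival under a year and chronic hemodialysis are all excluded. At low k the effect disappears or reverses once stays and deaths are allowed for. A one-sentence method statement does not forbid a scale or robust option in SAS. Only secondary outcomes are involved.

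Most of this stands, and it sets the limits of the point. At k of 0.25 or less with stays and deaths, there is no material inflation at 90 days. What does not fall away is the range k = 0.5-1, where inflation persists. A further set of runs that also let the hazard fall, so as to match both 28% at 30 days and 46% at 90 days, gave 4.6-4.9% at k = 0.25; across these variants k = 0.5-1 gave 5.9-10.4%. That the plan does not exclude a robust option is a reason to name one in advance, not to leave it open.

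A reader might infer several stronger things that the documents do not support:
- **Every total is anticonservative at every horizon.** The 30-day results fall on both sides of 5%.
- **Inflation must be at least as large at 180 days.** The plan gives no 180-day rate, and that argument ignores stays and deaths, which accumulate over the longer period.
- **The plan's own rates show strong heterogeneity.** A constant common rate fitted to 28% at 30 days would give 1 − 0.72³ = 62.7% at 90 days against the stated 46%. Attributing the whole gap to patient differences would require k of about 2.7. A hazard that falls after discharge explains the same gap with no overdispersion at all.
- **Missing rules on ED visits that end in admission, or on an exposure offset, add to the dispersion problem.** The first is an endpoint definition, and the case report form is not available to check. The second is a choice of estimand, since total events in a fixed window among all randomized patients is a legitimate target.

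**Conclusion.** The point holds as a conditional one. The only planned test of total HCRU relies on variance equal to mean, and the plan makes no provision if that fails for hospitalizations, ED visits or the combined total. The error at 90 days becomes material from k of about 0.5 upwards under the stay and death assumptions used here, and from about 0.25 if stays and deaths are ignored. The result rests on the gamma model, the plan's 46% rate, 7-day stays after every event and 5-10% of events ending the count; none of these beyond the 46% comes from the documents. The plan's rates come from a calculation for HF-related HCRU, so the all-cause totals have no figure of their own. The chi-square test of the primary endpoint, the 732 patients, and the first-occurrence and time-to-event analyses are untouched. The change is worth making because it is cheap and does not require knowing k.

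**What to change.** State in the Analyses section, before the data are analysed, that the hospitalization, ED and combined totals will be compared by Poisson regression with robust (sandwich) variance, and that rate ratios will be reported with 95% confidence intervals. Apply the same to the viewership comparisons of totals.

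The work is one variance option in the SAS model, with no change to design, data collection or sample size. The price is precision where counts are overdispersed. At 90 days intervals on the log scale widen by about 8-36% for k = 0.25-1 ignoring stays and deaths, and by about 4-17% for k = 0.5-1 with them. That is the width the data warrant. Where counts are underdispersed, intervals narrow by up to about 7% in the settings simulated.

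As optional clarifications, separate from this point, the plan could say whether an ED visit that ends in admission counts once or twice in the combined total, and whether the target is events per patient in the window or events per day of follow-up.
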